#### Final Analysis of the 4-week data

It is planned to keep sites open through at least the end of September 2017 in order to potentially achieve a total of 8 to 10 patients who are treated with BI 655130. Once a decision

has been made to stop further recruitment into the study then steps will be taken to prepare for the final analysis of the 4-week data.

The final analysis of the efficacy and safety data collected up to Week 4 will be performed once all entered patients have completed the first 4 weeks of study (i.e. through Visit 12); at that time point, a database lock will be done. The individual patient cut-off date for inclusion of data into the 4-week analysis will be the minimum of (actual cut-off date; date of dosing plus 38 days [representing the upper boundary of the time window for the Week 4 visit]); the actual cut-off date used for data cleaning purposes will be specified in the data cleaning plan for the 4-week analysis and will typically represent the date of attendance of the last patient to the Week 4 visit (i.e. date of performance of last Visit 12). Since the final analysis of the efficacy and safety data up to week 4 in this open-label trial will be complete, and because no further patient dosing visits are planned, the week 4 results may be made available and published to support enrolment into subsequent trials in this and potentially other indications of BI 655130. Analyses of the data described in the sections listed below will be performed at the time of database lock for the 4-week data:

- [Section 7](#) (Analyses of disposition, IPVs and analysis sets, up to Week 4)
- [Section 7.1](#) (Demographics and other baseline characteristics)
- [Section 7.2](#) (Historical medications, background medications, concomitant medication use, and medical/disease history)
- [Section 7.5.2.1](#) (Secondary efficacy endpoints up to Week 4, based on FAS and PPS)
- [Section 7.6.1](#) (Further efficacy endpoints up to Week 4, based on FAS)
- [Section 7.6.4](#) (Use of rescue medication up to Week 4, based on TS)
- [Section 7.7](#) (Extent of exposure)
- [Section 7.8.1](#) (Adverse events up to Week 4)
- [Section 7.8.2](#) (Laboratory data up to Week 4)
- [Section 7.8.3](#) (Vital signs including body temperature up to Week 4)
- [Section 7.8.5](#) (Injection site reactions)

Other selected data that will be displayed at time of the 4-week database lock includes:

- Plasma concentrations data

Some of the analyses performed at the time of the 4-week database lock may also be repeated following database lock for the entire trial (once all patients have completed the trial). The results for such endpoints obtained following the 4-week database lock should be considered the main source for interpretation on treatment effects over the first 4 weeks of study for the CTR; any differences in the outcomes obtained following the final database lock, if applicable, should be described.

Analysis of the complete trial data through Week 20

The analysis of the entire efficacy and safety, as well as biomarker, data including those data collected through the full 20 weeks of follow-up will be performed once all entered patients have completed the trial (up to Visit 14); at that time point, a final database lock will be done and all trial data will be reported.

#### **4. CHANGES IN THE PLANNED ANALYSIS OF THE STUDY**

The following analyses described in this TSAP are new/adapted analyses from those specified in the revised CTP.

- For secondary efficacy endpoints of a continuous nature, it was specified in the CTP that exact 95% confidence intervals around the mean will be produced. Per specification in [Section 7.5.2.1](#), the 95% confidence intervals for continuous data will be based on the t-distribution.

In the CTP it is stated that analyses of immunohistochemistry and flow cytometry will be conducted. These analyses will not be carried out for the CTR, but may be done at a later time point (depending on the obtained results). In case they are performed at a later time point, the analysis details will be described in a separate document.

In the CTP, it was noted that a logistics plan will be developed to protect the integrity of the trial data once the week 4 analyses has been performed. However, since at this time the final analysis of the efficacy and safety data up to week 4 will be complete, and because no further patient dosing visits are planned, the week 4 results may be made available and published to support enrolment into subsequent trials in this and potentially other indications of BI 655130.

The following analyses described in this TSAP are new/adapted analyses from those specified in the signed version of the TSAP, dated 4 OCT 2017:

- Section 6.2  
Definition of IPV: exclusion criteria 8 (i.e. use of restricted medication prior to the study) was modified from a programmatic to a manual assessment. This was done in order to ensure that medical decision could be made on whether such occurrence of an IPV would or would not affect the assessment on efficacy.

Same consideration was also applied to IPV D2.01 (and D2.02) representing prohibited medication use during the study.

- Section 6.6.2  
LOCF imputation was clarified to confirm that the baseline value would be carried forward in the event of no available post-baseline data (and not just in the case when missing post-baseline data was driven by rescue medication taken immediately after the first dose).
- Section 6.6.9  
Additional imputation strategies, for summary reporting only, are presented for the handling of cases where incomplete data are reported for previous GPP flare occurrences.

## **5. ENDPOINTS**

### **5.1 PRIMARY ENDPOINT**

**CTP:** Primary endpoint to assess safety and tolerability of BI 655130 is the number [N (%)] of patients with adverse reactions, defined as drug-related AEs.

### **5.2 SECONDARY ENDPOINTS**

#### **5.2.1 Key secondary endpoint**

Not applicable.

#### **5.2.2 Secondary endpoints**

##### **5.2.2.1 Secondary efficacy endpoints**

**CTP:** Secondary efficacy endpoints will be:

- Percent change [calculated as "reduction"] from baseline in GPPASI total score at Week 2
- Proportion of patients with GPPGA total score of 0 (clear) or 1 (almost clear) at Week 2
- Change from baseline in FACIT-Fatigue scale score at Week 2
- Change from baseline in Pain VAS score at Week 2

For details on calculating these scores at each visit, cf. [Section 9.1](#).

##### **5.2.2.2 Secondary pharmacokinetic endpoints**

Secondary PK endpoints are  $AUC_{0-\infty}$  and  $C_{max}$  of BI 655130 in plasma, as defined in Section 5.5.1.1 of the CTP.

## **6. GENERAL ANALYSIS DEFINITIONS**

### **6.1 TREATMENTS**

For basic study information on the treatment to be administered, assignment to treatment, and selection of dose, cf. Section 4 of the CTP.

All patients will receive one intravenous dose of 10 mg/kg of BI 655130 solution for infusion.

The following separate study phases are defined for analyses of efficacy, biochemical and cellular biomarkers, AEs, laboratory tests and vital signs:

**Table 6.1: 1 Flow chart of analysis phases for efficacy, biochemical and cellular biomarkers, AEs, laboratory tests and vital signs**

Study analysis phase	Description	Start (included)	End (included)
Screening phase	Screening	Earliest of (Date of informed consent, first screening procedure)	Date/time of start of infusion of study drug minus 1 minute
Treatment phase 	On-treatment period	Date/time of start of infusion of study drug (Day 1)	Date of end of infusion of study drug + 28 days at 11:59 p.m.
REP	On-treatment period	Date of end of infusion of study drug + 29 days at 12:00 a.m.	Date of end of infusion of study drug +140 days at 11:59 p.m.
Follow-up  phase	Off-treatment period	Date of end of infusion of study drug + 141 days at 12:00 a.m.	Latest of: i) Date of End-of-Trial visit (Week 20); ii) end date on trial termination page at 11:59 p.m.

Dates are defined individually per patient. If more than one date is associated with a specific visit, measurements associated with a specific date are assigned to a study analysis phase according to the rules specified in the table. An analysis phase will not extend beyond the start date of the subsequent phase.

 For the analysis of AEs, any AE occurrence on the same day as start of infusion of study drug will be assigned to the treatment phase.

 The follow-up phase only exists if the trial completion date is after the date of end of infusion + 140 days.

For the final analysis to be performed once all patients have completed through the planned first 4 weeks of trial, results will be summarized for the on-treatment period, unless otherwise specified. The selection of data for presentation in this analysis is described in [Table 6.7: 1](#).

For the entire analysis of the trial to be performed once all patients have completed through the planned 20 weeks of trial, results will be summarized for the on-treatment period, as well as for the off-treatment period, if applicable.

Analysis phases will be labelled as follows in statistical analyses:

- Screening phase: **Screening**
- On-treatment period: **BI 655130**
- Follow-up: **Follow-up**
- Total over the screening, on-treatment and follow-up periods: **Total**

CTR Section 15, Appendix 16.1.9.2.8.2 and Appendix 16.1.9.2.8.3 AE displays will present results for the on-treatment period. Screening and follow-up phases will not be included in this analysis.

CTR Appendix 16.1.9.2.8.1 displays will present results for the screening phase, on-treatment period, follow-up period, and total.

More details on the technical implementation of these analyses are provided in the ADS Plan of this TSAP.

## **6.2        IMPORTANT PROTOCOL VIOLATIONS**

Data discrepancies and deviations from the CTP will be identified for all patients in the database (i.e., enrolled patients). Consistency check listings (for identification of violations of time windows) and a list of protocol deviations will be provided to be discussed at the RPM/DBLM. At this meeting, it will be decided whether a discrepant data value can be used in analyses or whether it must be queried in the clinical database. Each protocol deviation must be assessed to determine whether it is an IPV. For definition of IPVs, and for the process of identification of these, refer to the BI reference document "Protocol Violation Handling Definitions" [\(2\)](#).

If any IPVs are identified, they are to be summarized into categories and will be captured in the RPM/DBLM minutes via an accompanying Excel spreadsheet [\(3\)](#). The following table contains the categories which are considered to be IPVs in this trial. If the data show other IPVs, this table will be supplemented accordingly by the time of the RPM/DBLM. Not all IPVs will lead to exclusion from analysis sets. IPVs leading to exclusion from analysis sets are indicated as such in [Table 6.2: 1](#).

IPVs will be summarized and listed.

Table 6.2: 1 Important protocol violations

Category / Code	Description	Comments	Excluded from
A	Entrance criteria violated		
A1	Inclusion criteria not met		
A1.01	Age out of range	Inclusion criterion 1, also check versus derived age	None
A1.02	"A known and documented history of GPP" not confirmed	Inclusion criterion 2	PPS, PKS, BMS, DSS, RSS
A1.03	"Presenting with a flare of GPP with at least 10% of BSA with erythema and pustules" not confirmed	Inclusion criterion 3	PPS
A1.04	GPPGA score showing a severity less than moderate	Inclusion criterion 4, also check calculated GPPGA at Visit 3	PPS
A1.05	For GPP patients receiving maintenance treatment with retinoids and/or methotrexate: maintenance treatment was received for less than 4 weeks prior to Visit 2.  For other GPP patients: patient received any maintenance therapy other than retinoids and methotrexate at Visit 2.	Inclusion criterion 5	PPS
A1.07	Women of childbearing potential did not agree to use effective method of birth control; male patients did not agree to use condoms	Inclusion criterion 7	None
A2	Exclusion criteria violated		
A2.01	Pregnancy	Exclusion criterion 1	None
A2.02	Immediate, life-threatening flare of GPP	Exclusion criterion 2	None
A2.03	Identified, ongoing serious/severe infection	Exclusion criterion 3	PPS
A2.04	Acute generalized exanthematous pustulosis (AGEP)	Exclusion criterion 4	PPS, PKS, BMS, DSS, RSS
A2.05	Differential diagnosis of toxic epidermal necrosis or Stevens-Johnson syndrome	Exclusion criterion 5	PPS, PKS, BMS, DSS, RSS
A2.06	Involved in or intending to participate in another investigational study during the course of this trial	Exclusion criterion 6	PPS, PKS, BMS, DSS, RSS

# PV will be detected manually.

Source: BI reference document 'Protocol Violation Handling Definitions' [001-MCS-50-413\_RD-01] (2).

Table 6.2: 1 Important protocol violations (continued)

Category / Code	Description	Comments	Excluded from
A2.07	Previous enrolment in this trial	Exclusion criterion 7	FAS  , PPS  , PKS, BMS  , DSS  , RSS 
A2.08a	Use of restricted medication with potential influence on efficacy data	Exclusion criterion 8, manual assessment of potential influence at RPM/DBLM	PPS, PKS, BMS, DSS, RSS
A2.08b	Use of restricted medication without potential influence on efficacy data	Exclusion criterion 8, manual assessment of potential influence at RPM/DBLM	None
A2.09	Patients with dose escalation of their maintenance therapy with methotrexate and/or retinoids within the 4 weeks preceding Visit 2	Exclusion criterion 9	PPS
A2.10	Background therapy with ciclosporin within the last 30 days preceding Visit 2	Exclusion criterion 10	PPS
A2.11	Previous exposure to an IL36R inhibitor	Exclusion criterion 11	PPS, PKS, BMS, DSS, RSS
A2.12	Severe, progressive or uncontrolled disease	Exclusion criterion 12	PPS
A2.13	Chronic or relevant acute infections	Exclusion criterion 13	PPS
A2.14	Patients with transplanted organ or who have ever received stem cell therapy	Exclusion criterion 14	PPS
A2.15	History of lymphoproliferative disease	Exclusion criterion 15	PPS
A2.16	Active or suspected malignancy or history of malignancy within 5 years prior to Visit 2	Exclusion criterion 16	PPS
A2.17	Evidence of a current or previous disease or medical condition other than GPP	Exclusion criterion 17	PPS
A2.18	History of allergy/hypersensitivity to a systemically administered biologic agent	Exclusion criterion 18	PPS
A2.19	Refusal to be hospitalized for 4 days following the infusion	Exclusion criterion 19	None

 The data reported during the second enrolment of the patient in the trial will be excluded.

# PV will be detected manually.

Source: BI reference document 'Protocol Violation Handling Definitions' [001-MCS-50-413\_RD-01] (2).

Table 6.2: 1 Important protocol violations (continued)

Category / Code	Description	Comments	Excluded from
B	Informed consent		
B1	Informed consent not available	Date of informed consent missing or no signature on patient's "Declaration of Informed Consent"  In this case: Patient's data will not be used at all.	All
B2	Informed consent too late	Informed consent date was after Visit 1	None
C	Trial medication		
C1	Incorrect trial medication		
C1.01	Study drug medication not taken	Patient entered but no study drug taken	TS, FAS, PPS, PKS, BMS, DSS, RSS
C2	Non-compliance		
C2.01	Non-compliance with study drug intake-- administered dose too high	Study medication dose is greater than 120% of the planned dose	PPS
C2.02	Non-compliance with study drug intake-- administered dose too low	Study medication dose is less than 70% of the planned dose	PPS, BMS, DSS, RSS
D	Concomitant medication		
D1	Previous medication		
D1.01	Washout of previous medication too short	Washout period too short - See Table 4.2.2.1: 1 in CTP	PPS, PKS #
D1.02	Rescue use on or after Visit 2 but prior to administration of study drug	Rescue medication taken on the day of Visit 2 or on the day of Visit 3 (clock time will not be reported)	FAS, PPS
D2	Prohibited medication use		
D2.01a	Use of prohibited med. on or after V2 or during the on-trt. period, unless rescue trt. to stabilize a worsening disease cond. – prior to or on D14, with potential influence on eff. data	See the list of restricted medication in CTP, Table 4.2.2.1: 1, manual assessment of potential influence at RPM/DBLM	PPS, PKS, BMS, DSS, RSS #

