7.3.2 Secondary analyses

The continuous secondary efficacy endpoints, such as GPPASI total score, Pain VAS, and FACIT-Fatigue score at week 2, will be evaluated descriptively, including the original as well as change from baseline values where applicable, along with exact 95% confidence intervals, if feasible. For the GPPASI total score, the percentage change from baseline at week 2 will be displayed.

The binary efficacy endpoint, GPPGA response of 0 (clear) or 1 (almost clear), will be described using patient frequencies and percentages. Exact 95% confidence intervals will additionally be provided for the proportion of patients with a response, if feasible.

The patient set for the evaluation of efficacy endpoints (FAS) will include all treated patients who had a baseline and at least one post-baseline measurement available for either GPPASI or GPPGA. Baseline is defined as the last measurement collected prior to administration of the trial treatment.

Proprietary confidential information © 2016 Boehringer Ingelheim International GmbH or one or more of its affiliated companies

The secondary PK parameters (refer to [Section 5.5.1](#)) will be calculated according to the BI Standard Operating Procedure (SOP) 'Standards and processes for analyses performed within Clinical Pharmacokinetics/Pharmacodynamics' ([001-MCS-36-472](#)). Analyses will be performed for parent drug.

Pharmacokinetic parameters of a patient will be included in the analysis unless the patient has an important protocol violation relevant for the evaluation. Whether a protocol violation is important will be decided no later than in the Report Planning Meeting.

Reasons for exclusion of single pharmacokinetic parameters may be:

- Time deviations
- Use of restricted medications

The patient set for the evaluation of PK endpoints (PKS) will include all treated patients that provide at least one observation for at least one secondary PK endpoint without important protocol violations with respect to the statistical evaluation of PK endpoints. It will be decided in the Report Planning Meeting which patients are to be included in the PKS.

Excluded patients will be listed with their individual plasma concentrations and individual pharmacokinetic parameters, however, will not be included in descriptive statistics for plasma concentrations, pharmacokinetic parameters or other statistical PK assessment.

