## **6.3 PATIENT SETS ANALYZED**

The following analysis sets will be defined for this trial:

- **Enrolled set (ES):**  
This patient set includes all patients who signed informed consent.  
It will be used for analyses of patient disposition.
- **Entered set (ENT-S):**  
This patient set includes all entered patients (as identified by the investigator in the eCRF), whether treated or not.  
It will also be used for analyses of patient disposition.
- **Treated set (TS):**  
This patient set includes all patients in the ENT-S who received study drug at Visit 3.  
It will be used for analysis of safety data.
- **Full analysis set (FAS):**  
This patient set includes all patients in the TS who had a baseline and at least one post-baseline measurement available for GPPASI or GPPGA without any IPV flagged for exclusion from the FAS in the table above.  
This is the main analysis set for presentation of efficacy.
- **Per protocol set (PPS):**  
This patient set includes all patients in the FAS who adhered to the CTP without any IPVs which are flagged for exclusion from the PPS in the table above.  
The PPS will be used for sensitivity analysis of secondary efficacy endpoints.
- **Pharmacokinetic parameter set (PKS):**  
This patient set includes all patients in the TS who provide at least one observation for at least one secondary PK endpoint, which was not flagged for exclusion. PK parameters (and blood and plasma concentrations) can be flagged for exclusion due to a protocol violation relevant to the evaluation of PK (to be decided no later than in the RPM) or due to PK non-evaluability (as revealed during data analysis, based on the criteria specified below). Exclusion of a patient's data will be documented in the CTR.  
Relevant IPVs are documented in [Table 6.2: 1](#) above.  
Plasma and blood concentrations and/or parameters will be considered as non-evaluable, if e.g. a pre-dose concentration is >5% of the  $C_{max}$  value of that patient, or if relevant time deviations occurred (as identified no later than in the RPM), or due to use of restricted medications (as identified no later than in the RPM).  
**CTP:** *It will be decided in the Report Planning Meeting which patients are to be included in the PKS.*  
This patient set will be used for the descriptive analysis of concentrations and PK parameters.

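### Does the SAP need a rule on whether a patient given under 70% or over 120% of the planned dose enters the Cmax and AUC summaries?

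*SAP*

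**What the plan says.** Two rows of SAP Table 6.2:1 deal with the amount of drug given. C2.01 applies when "Study medication dose is greater than 120% of the planned dose" and lists the per-protocol set (PPS) alone under the excluded sets. C2.02 applies when "Study medication dose is less than 70% of the planned dose" and lists PPS, BMS, DSS and RSS. The PKS appears in neither row.

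The surrounding text explains how to read the table. SAP 6.2 notes that not every important protocol violation (IPV) removes a patient from an analysis set, and that "IPVs leading to exclusion from analysis sets are indicated as such in" this table. SAP 6.3 defines the PKS, refers back to the table ("Relevant IPVs are documented in") and adds an open list of other grounds: "Plasma and blood concentrations and/or parameters will be considered as non-evaluable, if e.g. a pre-dose concentration" is too high relative to Cmax, or relevant time deviations or restricted medication occurred. It repeats the protocol's rule: "It will be decided in the Report Planning Meeting which patients are to be included in the PKS". SAP 7.5.2.2 includes every parameter in PKS analyses unless it is flagged.

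Protocol 7.3.2 admits patients to the PKS "without important protocol violations with respect to the statistical evaluation of PK endpoints", and leaves the meeting to decide which violations count as important.

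**The concern.** Cmax and AUC0-∞ are the secondary PK endpoints, and the trial describes them for one dose level, 10 mg/kg, in 6 to 10 patients. Both scale with the dose received, so a patient given half the dose does not describe exposure at 10 mg/kg. Yet a change in background methotrexate or retinoid dose up to Day 14 (D3.01) removes a patient from the PKS, while a large error in the study drug does not. Eleven rows name BMS, DSS and RSS together (A1.02, A2.04 to A2.07, A2.08a, A2.11, C1.01, C2.02, D2.01a, D3.01), and C2.02 is the only one that leaves out the PKS.

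A wrong dose is not far-fetched. Protocol 3.3.4.1 provides for infusions stopped early. Protocol 1.2.5 reports that a calculation error halved the dose of 3 subjects in the first-in-human trial, and that they were shown as a separate 0.05 mg/kg group. SAP section 3 has plasma concentrations displayed at the 4-week lock, so a decision on the PKS could be taken with concentrations known. At stake would be a summary pulled off target, or a choice that depends on the data.

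**Working it through.** **What the text implies.**

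1. SAP 6.2: sets from which a violation excludes are marked in Table 6.2:1.
2. SAP 6.3: the table is where the PKS-relevant violations are found.
3. C2.01 and C2.02 do not mark the PKS.
4. SAP 7.5.2.2: parameters that are not flagged are included.

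The default is therefore that a mis-dosed patient stays in. The meeting's power to depart from this comes from protocol 7.3.2 and the PKS definition, and it covers every patient and every violation. Adding the PKS to both rows would leave that power in place.

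The one-in-eleven pattern does not prove a slip. D1.01 ("Washout of previous medication too short") lists PPS and PKS without the biomarker sets, so the PKS was assigned separately from them.

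**Size, if one mis-dosed patient is kept.** The plan states no figure to reproduce. Inputs: n = 6 to 10 (protocol 7.6); the 70% and 120% limits (Table 6.2:1); first-in-human geometric CVs at 1, 3, 6 and 10 mg/kg with N = 6, 6, 6, 4 (protocol Table 1.2.5:2). Assumptions: log-normal exposure proportional to dose, with healthy men standing in for patients.

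With one of n patients at dose fraction f, the geometric mean changes by f^(1/n) − 1:

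| f | n = 10 | n = 8 | n = 6 |
|---|---|---|---|
| 0.70 | −3.5% | −4.4% | −5.8% |
| 1.20 | +1.8% | +2.3% | +3.1% |
| 0.50 | −6.7% | −8.3% | −10.9% |

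The 70% and 120% rows are the smallest effects, since the violations apply only beyond those limits. The 50% row matches the first-in-human error.

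*Spread.* Cmax CVs of 13.6, 7.17, 12.7 and 2.79%, turned into log-variances ln(1 + CV²) and weighted by 5, 5, 5 and 3 degrees of freedom, pool to 0.01109, a CV of 10.6%. One patient at f adds (ln f)²/n to the expected log-variance. At f = 0.70, (ln f)² = 0.1272, so the CV rises to 15.5% (n = 10), 16.5% (n = 8) or 18.1% (n = 6).

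*Against the standard error.* With the pooled variance, the standard error of the log mean is √(0.01109/10) = 0.033 or √(0.01109/6) = 0.043. The log shift |ln 0.7|/n is 0.036 or 0.059, which is 1.1 or 1.4 standard errors. With the variance that the contaminated sample would itself show (0.0238 at n = 10, 0.0323 at n = 6), the ratios are 0.73 and 0.81.

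*Would excluding such patients cure it?* A patient at 71% breaks neither limit and stays in under any reading. The shift is then 0.71^(1/n) − 1 = −3.4% (n = 10) to −5.5% (n = 6), almost the same as at 70%.

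**The case for a change.** The best argument for a change is that it is cheap and tidy. One sentence in SAP 6.3 could say that these patients stay in and that Cmax and AUC0-∞ are also shown per mg/kg actually given, a quantity already derived under SAP 7.7. The reasons for PK exclusion in the visible text do not mention dose, and the sponsor's own handling of the first-in-human error shows that pooling such patients was not thought right there.

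Part of this stands: no visible text gives the meeting a dose criterion, and a sentence would do no harm. The rest is weaker. The first-in-human trial was a dose-escalation study with dose group as the design factor; here there is one dose. Two opposite remedies are equally defensible (keep and normalise, or exclude and list), which marks a reporting choice and not an error. Keeping the patient can also save information, because the PKS serves all concentrations and PK parameters. Knowing the concentrations adds little risk: the trial is open-label and single-arm, the dose cut-offs are fixed in advance, and the pre-dose rule cannot be applied without concentrations. Finally, the further-PK sections are absent from the public SAP and the calculations are delegated to SOP 001-MCS-36-472. Dose normalisation may be covered there, so it cannot be called missing.

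**Conclusion.** No change is needed. Table 6.2:1 does leave the PKS out of C2.01 and C2.02, but the plan still has a default (the patient stays in) and a body able to depart from it. What is missing is a detail that analysts would fill sensibly once they saw the patient.

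They would see the patient. SAP 7.3 tabulates percent of planned dose in the same under-70% and over-120% categories, SAP 7.7 summarises mg/kg given, and SAP section 7 lists individual values and reports minimum, quartiles, median and maximum. Nothing formal rests on the result: protocol 7.2 plans no confirmatory test, 7.6 has no power basis and 5.8 plans no PK-PD analysis. A mis-dose is also made less likely by supervised administration (protocol 4.3) and the two-person check in protocol 4.1.4.

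If one patient at the 70% limit were kept, the raw geometric mean would move by −3.5% (n = 10) to −5.8% (n = 6); at half dose, by −6.7% to −10.9%. These figures assume exposure proportional to dose and exactly one such patient. With none, the effect is zero.
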